7.3 Description of Study Visits

7.3.1 Screening Visit

Visit 1 (0 – 28 days before therapy): The basic work-up will take place, including medical and sexual history, as well as necessary lab tests (testosterone, prolactin, hematology, chemistry), if not available during the last 12 months prior to screening. Subjects will complete the IIEF questionnaire. We will ensure that patients have 4 attempts for intercourse Screening visit can occur on same day as first injection + SWT. Refer to table 1 for procedures to be performed at the Screening visit.

7.3.2 Treatment Visits: Week 0 – Week 4

Upon evaluation of eligibility, subjects will be randomized to one of the two parallel study groups using an online program, and initiate treatment on the same day.

There will be 5 treatment visits for all groups, each occurring at weekly intervals (\pm 2 days), for a total duration of five weeks. Subjects will complete a Visual Analogue Scale (VAS) pain score after the end of each treatment. Refer to table 1 for all procedures to be performed at the treatment visits.

7.3.3 Follow Up Visits: Months 3 and 6 Post-Treatment

Follow up visits will occur within 90 \pm 14 days (Month 3) and 180 \pm 14 days (Month 6) days after final treatment visit. Refer to table 1 for procedures to be performed at the follow up visits visit.

8. Investigational Product

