INVESTIGATION PLAN	Autologous PRP injection + SWT therapy. All subjects in this group will receive 2 sessions of autologous PRP penile injection with 30 ± 7 day treatment interval. 5mL of PRP will be injected at each session. Additionally, patients will receive a total of 3600 shocks over a five-week period, starting at initial PRP injection.					
DURATION OF STUDY	7 months (1 month screening, 5 weeks of therapy sessions, 6 months of follow-up).					
DEFINITION OF ENDPOINTS	 Primary: Changes in markers of vasodilation (eNOS, nNOS), neo-angiogenesis (VEGF, CD-31), and systemic markers of endothelial function (EPCs, SDF-1α, and SCF). Secondary: Differences in Doppler ultrasound parameters (PSV and EDV) from baseline to 6 months post-therapy. Treatment satisfaction as assessed by EDITS questionnaire in all subjects. Incidence of Serious Adverse Events experienced up to 6 months post-therapy. 					
	 Exploratory: Change in IIEF-EF score from baseline to 3 and 6 months post-therapy. Percentage of subjects that achieve minimal clinically important difference (MCID) in IIEF-EF from baseline to 3 and 6 months post-therapy. Percentage of subjects who either decrease or discontinue use of PDE5i after three months post-therapy 					

Protocol Synopsis							
	1. Be Male						
	2. Be 30 to 80 years of age (inclusive).						
	3. Be able to provide written informed consent.						
INCLUSION	 Have a diagnosis of mild to moderate ED (12-21) or mild ED (22-25) based on IIEF-EF questionnaire score. 						
CRITERIA	 Have diagnosis of Diabetes Mellitus (Type 1 or Type 2), as documented by history of Hemoglobin A1C > 7% OR on medical therapy for Diabetes. 						
	6. Be in a stable relationship and have a minimum of 2 sexual attempts per month for at least one month prior to enrollment.						
	7. Agree to comply with all study related tests/procedures.						
	 Previous penile surgery of any kind (except circumcision and condyloma removal), such as penile lengthening, penile cancer surgery, penile plication, grafting. 						
	 Previous history of priapism, penile fracture, Peyronie's Disease, or penile curvature that negatively influences sexual activity, 						
	 Abnormal morning serum testosterone level defined as a value lower than 300 ng/dL (±5%). 						
	4. Psychogenic ED as determined by study investigator.						
EXCLUSION	5. Patients using ICI for management of ED						

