3.1 Primary Endpoints

- Changes in markers of vasodilation (eNOS, nNOS), neo-angiogenesis (VEGF, CD-31), and systemic markers of endothelial function (EPCs, SDF-1α, and SCF).

3.2 Secondary Endpoints (efficacy):

- Differences in Doppler ultrasound parameters (PSV and EDV) from baseline to 6 months post-therapy.
- Treatment satisfaction as assessed by EDITS questionnaire in all subjects.
- Incidence of Serious Adverse Events experienced up to 6 months post-therapy.

3.3 Exploratory Endpoints:

- Change in IIEF-EF score from baseline to 3 and 6 months post-therapy.
- Percentage of subjects that achieve minimal clinically important difference (MCID) in IIEF-EF from baseline to 3 and 6 months post-therapy.
- Percentage of subjects who either decrease or discontinue use of PDE5i after three months post-therapy

4. Study Location

The study will be funded by the CTSI pilot award (GR019191) and coordinated by the University of Miami (UM), Miller School of Medicine, Desai Sethi Urology Institute. All

study visits will take place in the Department of Urology clinics, (PAC: [name], University of Miami Miller School of medicine, Miami, FL. & Lennar: [name]) PRP preparation and SWT therapy administration will take place in the PAC andrology lab and clinic.

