6.4 Withdrawal Criteria

All subjects who either screen fails, is withdrawn from the study, or has completed all visits should be de-enrolled from the research database within 2 business days, in accordance with university policies (or respective institutional policy).

Subjects may be withdrawn from the study for any of the following reasons:

- a) A subject does not meet the eligibility criteria (the subject will be considered a screen failure).
- b) A subject withdraws consent.
- c) A subject expires during protocol participation from causes other than the study treatment (not due to adverse events).
- d) At the discretion of the principal investigator for issues of non-compliance, or other behavioral factors.

7. Procedures Involved

15 men with Erectile Dysfunction (ED) of organic origin, that meet all of the inclusion and none of the exclusion criteria, will be enrolled to receive PRP+SWT in an open-label fashion.

Autologous PRP injection + SWT therapy. All subjects in this group will receive 2 sessions of autologous PRP penile injection with 28 ± 2 day treatment interval. 5mL of PRP will be injected at each session. Additionally, patients will receive a total of 3600 shocks over a five-week period, starting at initial PRP injection.

7.1 Schedule of Events:

-

The events table for the conduct of this study is shown below:

Table1:

Schedule of Events		Screening			Follow Up				
Time Point		0-30 days	Week 0	Week 1	Week 2	Week 3	Week 4	Month 3	Month 6
Eve	nt	before randomization	Day 0	Day 7 ± 2	Day 14 ± 2	Day 21 ± 2	Day 28 ± 2	Day 90 ± 14	Day 180 ± 14
Infor	med Consent	x							
Dem	ographics	x							
Medi	cal History	x							
Phys	ical Exam	x							
Dopp	oler Ultrasound	x							X
aires	IIEF	x						X	x
tionna	EDITS							X	x
Ques	VAS		x	x	x	x	x		
Labo	ratory Tests*	x							
EPC	-CFUs	X						X	Х
Brac	hial FMD	X						Х	Х
PRP Injection			х				х		
Shockwave Therapy			Х	Х	Х	Х	Х		
Concomitant Medications/Therapy		x	x	х	х	x	x	x	x
Review Adverse Events			х	x	x	x	х	x	x

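### The Month 3 and Month 6 visits run on two clocks about 28 days apart: Table 1 counts from first treatment, Section 7.3.3 from the last

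*Combined protocol and SAP*

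**What the plan says.** - **Section 7.1, Table 1.** The columns read Day 0 (Week 0), Day 7 ± 2, Day 14 ± 2, Day 21 ± 2, Day 28 ± 2 (Week 4), Day 90 ± 14 (Month 3) and Day 180 ± 14 (Month 6). The second PRP injection and the fifth shockwave session are both in the Week 4 column. Nothing in the table as read says that the count restarts at follow-up.
- **Section 7.** The shockwave course is given "over a five-week period, starting at initial PRP injection", so Day 0 is the first treatment.
- **Section 7.3.2.** "There will be 5 treatment visits for all groups, each occurring at weekly intervals", with ± 2 days.
- **Section 7.3.3.** Month 3 and Month 6 are 90 ± 14 days and 180 ± "14 days (Month 6) days after final treatment visit". The section then sends the reader to Table 1 for the procedures.
- **Sections 3.2 and 3.3, and the synopsis.** Doppler parameters are compared "from baseline to 6 months post-therapy". The safety endpoint is "Incidence of Serious Adverse Events experienced up to 6 months post-therapy". The exploratory endpoints include "Change in IIEF-EF score from baseline to 3 and 6 months post-therapy".
- **Synopsis, duration.** "7 months (1 month screening, 5 weeks of therapy sessions, 6 months of follow-up".

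No section says which count governs.

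**The concern.** The same numbers, 90 ± 14 and 180 ± 14, are attached to two starting points four weeks apart. Staff need both places to run a visit: Section 7.3.3 for the timing and Table 1 for the procedures.

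If visits are booked from Table 1, the IIEF, EDITS, EPC-CFU and brachial FMD measurements at both visits, and the Doppler at Month 6, are taken about a month earlier after therapy than the visit names suggest. For Doppler, IIEF-EF and serious adverse events this contradicts the endpoint definition itself. The primary endpoint includes EPCs and states no time point; the EPC-CFU assay is timed only through these two visits, so the ambiguity reaches a primary measure as well. Table 1 puts the last adverse event review at Month 6, which on its own count comes before the safety period closes.

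If some of the 15 men are booked by one rule and some by the other, time since therapy varies between them for no clinical reason, and a visit that is on time under one rule is usually a deviation under the other.

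**Working it through.** **Inputs.** Last treatment day F = 28, range 26 to 30 (Table 1). Follow-up targets of 90 and 180 days, each ± 14 (Table 1 and Section 7.3.3). One month = 365.25/12 = 30.44 days.

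**Step 1. Windows on the Day 0 axis.** Table 1 gives 90 ± 14 = Day 76–104 and 180 ± 14 = Day 166–194. Section 7.3.3 gives F + 76 to F + 104 and F + 166 to F + 194.

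| Last treatment | Month 3, Table 1 | Month 3, 7.3.3 | Month 6, Table 1 | Month 6, 7.3.3 | Shared days per visit |
|---|---|---|---|---|---|
| Day 26 | 76–104 | 102–130 | 166–194 | 192–220 | 3 |
| Day 28 | 76–104 | 104–132 | 166–194 | 194–222 | 1 |
| Day 30 | 76–104 | 106–134 | 166–194 | 196–224 | 0 |

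The gap between the clocks is F itself, 26 to 30 days. A ± 14 day window is 28 days wide.

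**Step 2. Time since therapy if Table 1 is followed.**
- Nominal, F = 28: 90 − 28 = 62 days (2.04 months) and 180 − 28 = 152 days (4.99 months).
- Month 3 range: 76 − 30 = 46 to 104 − 26 = 78 days.
- Month 6 range: 166 − 30 = 136 to 194 − 26 = 168 days.

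The last adverse event review therefore falls 180 − 168 = 12 to 180 − 136 = 44 days short of 180 days, nominally 28.

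**Step 3. Both clocks in use.** Section 7.3.3 allows Month 6 at 166 to 194 days after therapy. Adding Table 1's 136 to 168 gives 136 to 194, a spread of 58 days against the 28 planned.

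**Step 4. Other readings of the last treatment day.**
- If the ± 2 days of Section 7.3.2 accumulates over four intervals, F runs from 28 − 8 = 20 to 28 + 8 = 36. The windows then share 9 days at F = 20 and none at F = 36. The latest Table 1 Month 6 visit is 194 − 20 = 174 days after therapy.
- The synopsis gives a PRP interval of 30 ± 7 days where Section 7 gives 28 ± 2, a difference that itself needs reconciling. With 30 ± 7, F runs from 23 to 37. The windows share 6 days at F = 23 and none at F = 37, and the latest Month 6 visit is 194 − 23 = 171 days after therapy.

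No reading of F brings the Section 7.3.3 rule back to Day 90 and Day 180.

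**Step 5. Does the synopsis duration settle it?**
- Listed parts in sequence: 30 + 28 + 180 = 238 days (7.82 months), or with five full weeks 30 + 35 + 180 = 245 days (8.05 months). The stated total is 7 months.
- Table 1 count with full screening: 30 + 180 = 210 days (6.90 months).
- Post-therapy count with screening on the day of first treatment: 28 + 180 = 208 to 35 + 180 = 215 days (6.83 to 7.06 months). Section 7.3.1 allows this: "Screening visit can occur on same day as first injection + SWT".

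Seven months fits either clock, so the duration does not decide between them. It does not equal the sum of its own parts.

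**The case against.** The strongest reply is that there may be only one clock. Table 1 never says in words that follow-up is counted from first treatment. Follow-up is a separate block, the screening column has its own reference point, and the table's header row did not survive extraction well. If the block restarts the count after therapy, the conflict disappears, and the title of Section 7.3.3 and the endpoint wording both point that way. But this supposes a label that the text does not show. The columns run on from Day 28 to Day 90 in the same unit, and a reader of the table would count them so. If a restart was meant, the table needs to say it.

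Some narrower points do stand:
- The 26 to 30 day gap, and the 46–78 and 136–168 day ranges, hold for Table 1's own Day 28 ± 2 and widen under the readings in Step 4.
- Section 7.3.3 itself accepts a Month 6 visit at 166 days, so a few late Table 1 visits comply with both rules, and a compliant Section 7.3.3 visit can also be up to 14 days short of 180. The difference is that Section 7.3.3 centres on 180 days, whereas no Table 1 visit reaches it.
- The marker and EDITS endpoints state no time point, so for them only the meaning of the visit name is in doubt.
- The Day 0 count with full screening gives 6.90 months, so the synopsis total cannot be held against Table 1.

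**Conclusion.** The concern holds. Table 1 and Section 7.3.3 place the same visits about 28 days apart, and the windows are too narrow to absorb the gap: they share one day, three days or none for a last treatment on Day 28, 26 or 30. Following Table 1 puts the nominal visits at 2.0 and 5.0 months after therapy. No Month 6 visit reaches 180 days after therapy under any reading of the treatment windows; the maximum is 174 days.

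This rests on reading Table 1 as one continuous axis, which is how it is printed in the text available. Because Section 7.3.3 and the timed endpoints agree with each other, the Table 1 labels are the odd ones out, although no section states a precedence. The consequence is limited: it concerns when outcomes are measured and what the results may be said to describe. With a single arm there is no between-group comparison to bias.

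**What to change.** Choose one time origin and use it in Table 1, Section 7.3.3, the synopsis and the endpoint definitions.

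- **Post-therapy clock (least text to change).** Relabel the two follow-up columns of Table 1 as 90 ± 14 and 180 ± 14 days after the last treatment visit, with a note that these are about Day 118 (28 + 90) and Day 208 (28 + 180) from first treatment. Restate the synopsis duration as at most about 8 months per participant, including up to one month of screening.
- **Day 0 clock.** Correct Section 7.3.3 and reword the timed endpoints as 3 and 6 months after first treatment.

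The first route costs two column labels and one synopsis line. If visits are being booked from Table 1, it lengthens follow-up by about four weeks per man; if they already follow Section 7.3.3, conduct does not change.

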8.2 Administration of Investigational Therapies

8.2.1 Platelet-Rich Plasma

The patient will be positioned supine. A sterile field will be developed with Betadine prep of the genitalia, sterile gloves and a sterile extremity drape. A total of 20 mL of 1% lidocaine will be drawn up using an 18-gauge needle and will be subcutaneously administered using a 27-gauge needle into the subcutaneous tissue at the base of the penis to obtain a dorsal nerve block. A 1/4inch Penrose drain will be used as a tourniquet by placing it at the base of the penis and maintaining it in place under tension by a sterile clamp. A maximum of 5 mL of PRP will be infused steadily over a two-minute period – approximately 2.5 mL each into the right and left

corpus cavernosum, as shown in Figure 1. The injections will be performed at this slow speed (each side over 2 minutes of infusion) to minimize injury to the platelet cells. In the control arm, men will be administered injectable normal saline that will be injected in a similar manner as the PRP.

Following administration of PRP or normal saline, compression of the penis will be achieved with a clenched fist for 20 minutes. At 20 minutes, the tourniquet will be removed, and a compressive dressing will be placed around the penile shaft. The patient will be instructed to remove the compression bandage in 4 hours and to contact the study coordinators if he experiences any problems.

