11.1 Adverse Events (AEs)

An adverse event (AE) is defined as any untoward medical occurrence associated with the use of a drug in humans, whether or not considered drug related. An AE can be any unfavorable and unintended sign (including an abnormal laboratory finding), symptom, or disease temporally associated with the study. The event does not need to have a causal relationship with treatment. Common Terminology Criteria for Adverse Events Version 5 (CTCAE) will be used for describing AEs. All urological and/or reproductive system AEs will be recorded. For all other AEs, only events greater than grade 2 will be recorded.

Based on our own pilot data assessing SWT and PRP monotherapy, we have compiled the following data on adverse events (Table 2):

We anticipate there to be few adverse events related to the study. Based on the four published studies and abstracts, including 75 men, only minor adverse events were reported (Bruising 1, Mild Pain 4). No serious adverse events were observed [23-26].

SWT related adverse events	
Transient mild cutaneous purpura	0.10%
Local erythema	0.50%
Local swelling/edema	1.00%
Transient local anesthesia or paranesthesia	1.10%
Transient local anestnesia of paranestnesia	1.10/0

PPR related adverse events					
Pain greater than 5/10 at time of injection	5.00%				
Pain lasting > 5 days	5.00%				
Penile bruising	0.00%				
Penile fracture	0.00%				

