13.1 Risks to Subjects

We anticipate there to be few adverse events related to the study. Based on the four published studies and abstracts, including 75 men, only minor adverse events were reported (Bruising 1, Mild Pain 4). No serious adverse events were observed [23-26]. After literature review, we believe this product to be of non-significant risk to patients (NSR) and for investigational use in a clinical study protocol.

Based on published studies, we will record anticipated adverse events to patients include: local injection site reaction, penile pain, penile hematoma (bleeding into the tissue), penile swelling, allergic reaction to the anesthetic, local infection, penile fracture, or new penile curvature. In addition, there may be uncommon or previously unknown risks that might occur. We will record every adverse event at every visit systematically.

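### No adverse event review is scheduled between the Week 4 visit (second PRP injection, fifth shockwave session) and Month 3, so delayed or prolonged non-serious local events could be under-recorded

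*Combined protocol and SAP*

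**What the plan says.** Section 7 plans 15 men in a single group who "will be enrolled to receive PRP+SWT in an open-label fashion", with "2 sessions of autologous PRP penile injection with 28 ± 2 day treatment interval". The synopsis gives a different spacing: "2 sessions of autologous PRP penile injection with 30 ± 7 day treatment interval".

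The Schedule of Events (Section 7.1, Table 1) puts PRP at Week 0 and Week 4 and shockwave at every visit from Week 0 to Week 4. Its row "Review Adverse Events" is marked at Days 0, 7, 14, 21 and 28, then at Month 3 and Month 6. The visual analogue pain scale (VAS) is marked at the five treatment visits, and Section 7.3.2 places it at the end of each treatment.

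The follow-up clock is stated in two ways. Table 1 gives Month 3 as Day 90 ± 14 on an axis where Day 0 is the first treatment. Section 7.3.3 counts the same 90 ± 14 days (and 180 ± 14 for Month 6) from the end of treatment: "Month 6) days after final treatment visit".

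On capture of events, Section 13.1 says "We will record every adverse event at every visit systematically". Section 11.1 requires every urological or reproductive event to be recorded, whatever its grade. Between visits the only provision is in Section 8.2.1: "The patient will be instructed to remove the compression bandage in 4 hours and to contact the study coordinators if he experiences any problems". No scheduled call or diary is described.

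**The concern.** The two injections are not followed up alike. After the first, the man is asked about adverse events about a week later and weekly after that. After the second, given on the same day as the last shockwave session, nobody is scheduled to ask him again for about two to three months.

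Many of the local events that the protocol names can begin and end within that interval. Table 2 in Section 11.1 lists "Pain lasting > 5 days" at 5.00% in the sponsor's own pilot data, and Sections 11.1.1 and 13.1 add bruising, swelling, haematoma and local infection. Onset, CTCAE grade and days of pain are hard to reconstruct after such a delay.

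At stake is the description of local tolerability. The synopsis makes the incidence of adverse events part of the secondary objective, and Section 1.4 presents the combination as not yet evaluated.

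**Working it through.** The plan states no figure for this gap, so there is none to reproduce. The check is visit-window arithmetic.

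**Inputs**
- Second injection and fifth shockwave session: Week 4, Day 28 ± 2, so Day 26 to 30 (Table 1; same spacing in Section 7).
- Month 3 counted from Day 0: Day 90 ± 14, so Day 76 to 104 (Table 1).
- Month 3 counted from the final treatment visit: 90 ± 14 days (Section 7.3.3).
- First review after the first injection: Day 7 ± 2 (Table 1).
- Alternative spacing of injections: 30 ± 7 days, so second injection on Day 23 to 37 (synopsis).

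**Gap from the second injection to the next scheduled review**

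| Reading | Shortest | Nominal | Longest |
|---|---|---|---|
| Table 1 clock, 28 ± 2 | 76 − 30 = 46 | 90 − 28 = 62 | 104 − 26 = 78 |
| Section 7.3.3 clock | 90 − 14 = 76 | 90 | 90 + 14 = 104 |
| Table 1 clock, synopsis 30 ± 7 | 76 − 37 = 39 | 90 − 30 = 60 | 104 − 23 = 81 |

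The Section 7.3.3 row takes the second injection to be given at the final treatment visit, as Table 1 shows.

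**Gap after the first injection:** 7 − 2 = 5 to 7 + 2 = 9 days.

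**Share of sessions affected:** 15 men × 2 sessions = 30, of which 15 (half) are second sessions. The same interval follows the last of the five shockwave sessions.

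**What the Week 4 visit itself covers.** The VAS and the adverse event review marked that day can pick up pain at injection and other immediate reactions. They cannot pick up pain that lasts beyond 5 days, later bruising or swelling, a haematoma that develops afterwards, or infection. For these, the plan relies on the man's own call or on his memory at Month 3.

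**The case against.** The strongest reply is that the consequence is limited. The primary endpoint is a set of biomarkers. The only listed safety endpoint is serious adverse events up to 6 months (Section 3.2); such events are unlikely to be forgotten, and reviews at Months 3 and 6 cover that period. Duration of local events is not an endpoint, and no comparison of the first injection with the second is planned. The reviews at Days 7 to 21 coincide with the weekly shockwave visits and are not presented as dedicated post-injection checks. Section 13.1 promises recording at visits, which Table 1 provides from Week 0 onward. All of this stands, and it makes the point a modest one. It does not remove it: adverse event incidence is in the synopsis secondary objective, and Section 11.1 asks for all urological and reproductive events, not only those at hand on a visit day.

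Three stronger readings are tempting and are not supported.
- A reader might infer that the second injection has no safety check at all. The same-day VAS and review at Week 4 cover immediate events, including severe pain at injection, one of the two PRP events with a non-zero rate in Table 2.
- A reader might join the two clocks into a single gap of 46 to 104 days. No one reading of the schedule gives that range; each clock has its own.
- A reader might turn the 5.00% for prolonged pain into a probability of missed events. Table 2 does not say whether the rate is per man or per injection, and any such figure would be the chance that an event occurs, not that it goes unrecorded. Table 2 also gives penile bruising as 0.00%, although Section 11.1 cites one case among 75 men in published work.

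**Conclusion.** The point holds for delayed or prolonged non-serious local events after the second injection and the fifth shockwave session. No review is scheduled for 62 days (46 to 78) on the Table 1 clock or 90 days (76 to 104) on the Section 7.3.3 clock, against 5 to 9 days after the first injection. The synopsis spacing would lower the Table 1 minimum to 39 days, so the conclusion does not depend on which reading is adopted.

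The incidence, grade and duration of these events could be under-recorded. The documents do not show that they would be: a man may call, and events may be recalled at Month 3. How much would be lost cannot be estimated from the documents. The serious adverse event endpoint is little affected, and the trial's validity is not in question. This is a worthwhile and inexpensive improvement. It rests on reading Table 1 as the complete list of scheduled contacts; no other section describes one.

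**What to change.** Add one scheduled adverse event contact by phone, made by the existing study coordinator, about 7 days after the Week 4 visit. Use the same adverse event questions as at the visits, plus the number of days of pain. Show it as a new column in Table 1 with a mark in the adverse event row.

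In the same amendment, reconcile the follow-up clock between Table 1 and Section 7.3.3, and the injection spacing between the synopsis and Section 7, so that the timing of each review is defined once.

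The cost is about 15 short calls (one per man) and the amendment itself, with no added procedure or staff. Recorded event rates may look slightly less favourable because more mild events would be captured.
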